## A. OBJECTIVES

The objective of this National Institutes of Health (NIH)-funded proposal is to characterize potential gender differences when switching from combustible cigarettes (CCs) to nicotine and placebo experimental electronic cigarettes, the National Institute on Drug Abuse's (NIDA) Standard Research E-Cigarettes (SRECs). We propose the following aims:

**Aim 1. To characterize the effects of switching to nicotine vs. placebo SRECs from CCs on product use, product acceptability, reinforcement, and nicotine dependence symptoms among adult daily CC smokers.** We hypothesize that nicotine-containing SRECs (SREC-NIC; 5%; ~59 mg/ml nicotine) will lead to decreases in CC-specific measures, decreases in withdrawal symptoms, and increases in electronic cigarette (EC)-specific use, acceptability, and reinforcement compared to placebo SRECs (SREC-PLA; 0 mg/ml nicotine). The primary outcome measure for Aim 1 will be CPD.

**Aim 2. To characterize the differences between male and female CC smokers when switching to nicotine vs. placebo SRECs from CCs on product use, product acceptability, reinforcement, and nicotine dependence symptoms.** We hypothesize that men, compared to women, will show more product use, acceptability, and reinforcement with SREC-NIC, relative to SREC-PLA, but that women will show overall less SREC use, and less CC reduction, than men. The primary outcome measure for Aim 2 will be CPD.

**Exploratory Aim: To characterize which factors moderate or mediate the effects of switching to nicotine and placebo SRECs from CCs among male and female CC smokers.** In an exploratory fashion, we will examine whether baseline factors, including prior EC exposure/ flavor preference, menthol CC preference, nicotine dependence, exposure (nicotine, cotinine, anabasine), hormonal contraception use, age, and race/ethnicity, moderate the Aims 1 & 2 hypotheses. We will also examine the mediating effects of product satisfaction, menstrual phase, and smartphone-collected withdrawal, craving, affect, product use on these hypotheses.

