During all phases, participants will complete SMS-prompted once daily smartphone Qualtrics assessments of product use (CPD, number of EC episodes [Phases 2 & 3], other tobacco use) and 2 daily random assessments of nicotine dependence symptoms (withdrawal, craving, and affect; see Assessment of Product Reinforcement, below). For the daily assessments of product use, the SMS will arrive on the participant's smartphone approximately 2 hours before his or her self-determined bed time, and will contain a link to a questionnaire provided through MD Anderson's Qualtrics survey platform. The random EMA assessments of nicotine dependence symptoms will be restricted to 2 instances per day to limit participant burden. To do so, each day will be divided into 2 blocks, based on each participant's reported wake and bed time that is collected at the screening visit (see Appendix X). Our SMS/Qualtrics backend software, running on a Microsoft SQL Server, will prevent random assessments from occurring within 2 hours of other assessments. The *primary* outcome measure of Aims 1 & 2, CPD, will come from the smartphone daily diary data of CC use over the past 24 hours. TLFB collected at each phase will be used as a secondary source of CC use to supplement missing smartphone daily diary data.

The total time to complete the once daily product use and 2 random EMA assessments of nicotine dependence symptoms will be approximately 15-20 minutes/day. Our previous

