research has obtained EMA compliance rates of >75% and found EMA reactivity to be nonexistent or small. We have extensive experience implementing and developing EMA programs and analyzing EMA data related to smoking behavior and anticipate no issues in carrying out this aspect of our proposal. Because prompts may occur at inconvenient times (e.g., driving), participants will be instructed that they can delay responding for up to 90 minutes, and they will receive a "missing assessment" SMS reminder if they fail to complete a daily or random assessment within 90 minutes of it being sent. The SMS/Qualtrics app will provide feedback on percentage of completed assessments, as well as compensation earned (see Recruitment and Retention Plan, above). We have successfully used this SMS/Qualtrics platform to collect similar EMA data in our current EC/VLNC product switching grant (2015-0638). Participants without a smartphone, or who would prefer not to use their own device, will be provided with a smartphone and service plan for the duration of the study. Given that 77% of adults own smartphones, as of 2016, we anticipate that relatively few participants will need a study smartphone.

**Assessment of product acceptability.** As part of Aims 1 & 2, product acceptability will be evaluated in terms of explicit product liking, perceived product harm, and implicit product liking (i.e., attitudes) at the end of each phase. Explicit product liking will be measured using Product Evaluation Scales (PES), which are modified versions of the Cigarette Evaluation Scale (CES). The CES is an 11-item questionnaire that evaluates the cigarette smoking experience in terms of satisfaction, tastiness, dizziness, ability to calm, concentration, wakefulness, reduction of hunger, nausea, irritability, enjoyment of sensations of smoke, and craving reduction. We will use 2 product-specific versions of the PES to evaluate CC and SREC product liking (with SRECs evaluated at weeks 4 & 6 only; see Appendix M).

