**Hypothesis Testing: Aim 1. To characterize the effects of switching to nicotine vs. placebo SRECs from CCs on product use, product acceptability, reinforcement, and nicotine dependence symptoms among adult daily CC smokers.** Assessments will include: product use (CPD, number of EC vaping sessions, nicotine, cotinine, minor tobacco alkaloids); product acceptability (explicit product liking, implicit product liking, and perceived product harm); reinforcement (RRE) and nicotine dependence symptoms (withdrawal, craving, and affect). We hypothesize that SREC-NIC will lead to decreases in CC-specific measures (CPD, minor tobacco alkaloids, and CC dependence), decreases in withdrawal symptoms, and increases in EC-specific use, acceptability, and reinforcement compared to SREC-PLA. The primary outcome measure for Aim 1 will be CPD.

**Hypothesis Testing: Aim 2. To characterize the differences between male and female CC smokers when switching to nicotine vs. placebo SRECs from CCs on product use, product acceptability, reinforcement, and nicotine dependence symptoms.** This aim will examine the moderating role of gender on the impact of SREC type on the assessments described in Aim 1. We hypothesize that men, compared to women, will show more product use, acceptability, and reinforcement with SREC-NIC, relative to SREC-PLA, but that women will show overall less SREC use, and less CC reduction, than men. The primary outcome measure for Aim 2 will be CPD.

**Exploratory Aim: To characterize which factors moderate or mediate the effects of switching to nicotine and placebo SRECs from CCs among male and female CC smokers.** In an exploratory fashion, we will examine whether baseline factors, including prior EC exposure and prior flavor preference, menthol CC preference, nicotine dependence, baseline TNE, and race/ethnicity, moderate the Aims 1 & 2 hypotheses. We will also examine the potentially mediating effects of product satisfaction, hormonal contraception use, menstrual phase, and smartphone-collected withdrawal, craving, affect, product use on these hypotheses.

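### SREC satisfaction is listed as a mediator but rated only after each phase's cigarettes per day have accrued, so mediation could not be told apart from the reverse

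*Combined protocol and SAP*

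**What the plan says.** Section A (Objectives, Exploratory Aim) states: "We will also examine the mediating effects of product satisfaction". The Exploratory Aim under Statistical Approach & Expected Outcomes repeats this slightly more cautiously: "We will also examine the potentially mediating effects of product satisfaction". The same sentence adds smartphone-collected withdrawal, craving and affect. The effects to be mediated are those of the Aims 1 and 2 hypotheses. For Aim 1, "The primary outcome measure for Aim 1 will be CPD", and Aim 2 has the same primary outcome.

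The only satisfaction measure described is an item of the Product Evaluation Scale, adapted from a questionnaire that "evaluates the cigarette smoking experience in terms of satisfaction, tastiness, dizziness" and other qualities. Under Assessment of product acceptability, the measures run through "implicit product liking (i.e., attitudes) at the end of each phase". The scale is used "with SRECs evaluated at weeks 4 & 6 only; see Appendix M", so each SREC phase has one rating, at its close.

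Under Assessment of product use, primary CPD "will come from the smartphone daily diary data of CC use over the past 24 hours", collected every day of each two-week phase. The twice-daily smartphone prompts use eight items drawn from the craving, affect and withdrawal scales, and no satisfaction item is described. The plan gives no mediation model, lag or sensitivity analysis.

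**The concern.** A mediator has to come before the outcome it is meant to explain. Here the diary days of an SREC phase come first and the satisfaction rating follows. Someone who replaced many cigarettes may rate the SREC as satisfying for that reason. The phases run back to back, so no later CPD under the same product remains for the rating to explain. The week-4 rating does precede Phase 3 CPD, but it concerns the other SREC.

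The crossover does not cure this. Randomisation protects the effect of SREC type on satisfaction and its effect on CPD. It does not protect the path from satisfaction to CPD, which is the path a mediation claim needs.

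What is at stake is an explanation, not a treatment comparison. Future directions says the project will identify factors that moderate or mediate the switching effects. A statement that nicotine lowers smoking through satisfaction could rest on data that fit the opposite direction equally well.

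**Working it through.** **1. Order of measurement in an SREC phase**

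| Quantity | When | Where stated |
|---|---|---|
| CPD | daily, weeks 3–4 and 5–6 | Assessment of product use |
| SREC satisfaction | once, week 4 and week 6 | Assessment of product acceptability; Phases 2 & 3 |

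Power and Sample Size refers instead to CPD from the timeline follow-back interview. That interview covers the time since the previous visit, so the order is the same with either source.

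**2. Scale from the plan's own power figures**

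The plan gives 80% power for 1.75 CPD (main effect) and 3.5 CPD (gender interaction) with n = 140. It states neither an SD nor an alpha. Assuming two-sided alpha 0.05:

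- Implied SD of the within-person nicotine-minus-placebo difference: 1.75 × √140 / (1.960 + 0.842) = 20.71 / 2.802 = 7.39 CPD.
- Check on the interaction, 70 men and 70 women: 2.802 × 7.39 × √(2/70) = 3.50 CPD. The two stated figures agree with each other.

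**3. Illustration with no effect of satisfaction on CPD**

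For each participant, CPD difference C = −1.75 + 7.39z. Satisfaction difference in SD units M = −r·C/7.39 + √(1 − r²)·e + d. Here z and e are independent standard normal, r is the strength of the path from CPD to satisfaction, and d is a direct effect of nicotine on satisfaction. The documents give neither r nor d. Mediation is declared when the mean of M and the slope of C on M both have p < 0.05.

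Share of trials declaring mediation (approximate):

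| r | d = 0 (reverse causation only) | d = 0.2 SD | d = 0.3 SD |
|---|---|---|---|
| 0.2 | 6% | 55% | 66% |
| 0.3 | 13% | 84% | 94% |
| 0.4 | 19% | 93% | 99% |

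The expected CPD wrongly assigned to satisfaction is (r × 1.75/7.39 + d) × (r × 7.39):

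- r = 0.2, d = 0: 0.047 × 1.478 = 0.07 CPD.
- r = 0.4, d = 0: 0.095 × 2.956 = 0.28 CPD.
- r = 0.2, d = 0.2: 0.247 × 1.478 = 0.37 CPD.
- r = 0.4, d = 0.3: 0.395 × 2.956 = 1.17 CPD.

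The first column is low because reverse causation alone moves mean satisfaction by only 0.05 to 0.09 SD, which 140 people rarely detect. The other columns depend on d.

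**4. Does a simple lag solve it?**

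Not by itself. Week-1 CPD can drive both a week-1 mediator and week-2 CPD. With an assumed week-to-week correlation of 0.7 in the CPD differences, r of 0.2 to 0.4 and d of 0.2 to 0.3 SD, a week-1 mediator with week-2 CPD still declares mediation in about 32 to 92% of trials. Adding week-1 CPD as a covariate brings this to about 4 to 5%.

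**The case against.** The strongest reply is that the plan claims little. The aim is exploratory, the statistical section says only that the effects are potentially mediating, and no mediation test is specified, so the joint-significance rule above is the reviewer's choice. That stands. A reader might infer that reverse causation will be reported as mediation. The documents do not support this, because they fix neither the model nor the wording of the report. What they do support is that the two directions could not be separated.

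A reader might also infer that the timing alone produces false mediation in most trials. It does not: reverse causation alone gives about 6 to 19% under these assumptions. The higher range needs a direct effect of nicotine on satisfaction. Its direction matches the Aim 1 hypothesis of greater acceptability with nicotine, but its size is assumed.

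On the smartphone measures, silence about order is not a design defect. Symptoms are prompted twice a day and CPD once a day for 42 days, so a lagged analysis is already possible. This stands, and it makes the request one of specification only.

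The mediation sentence also covers outcomes other than CPD, and the documents never say outright that product satisfaction means the SREC item of the scale. But CPD is the primary outcome, no other satisfaction measure is described, and cigarette ratings at weeks 0 and 2 precede SREC exposure and so cannot mediate its effect.

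The exploratory label lowers the weight given to a result. It does not make its direction identifiable, and neither a larger sample nor the false discovery rate adjustment would.

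**Conclusion.** The point holds as one of interpretation. With satisfaction rated only at the end of each SREC phase, a mediation finding for CPD could not be distinguished from reduced smoking raising satisfaction. This conclusion rests on the timing alone and needs no assumed figure.

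The size is illustrative: about 6 to 19% of trials with reverse causation only, and about 55 to 99% with an added direct nicotine effect of 0.2 to 0.3 SD. Both ranges assume n = 140, a 1.75 CPD effect, a difference SD of 7.39, two-sided alpha 0.05 and r of 0.2 to 0.4.

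It would be wrong to infer that the Aim 1 or Aim 2 primary comparisons are compromised: they do not use satisfaction as a mediator and are untouched. This is a cheap improvement to an exploratory analysis.

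**What to change.** In Section A and in the Exploratory Aim of the statistical section, remove end-of-phase product satisfaction from the mediators of CPD and report it as the acceptability outcome it already is under Aims 1 and 2. Alternatively, keep the analysis and label the relation to CPD as an association only.

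For smartphone withdrawal, craving and affect, specify a time-ordered model that adjusts for prior CPD. One form takes the week-1 average of each SREC phase as mediator, week-2 CPD as outcome and week-1 CPD as covariate. Another is a day-level lagged model that adjusts for prior-day CPD.

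If satisfaction is still wanted as a mediator, add one satisfaction item to the existing daily survey and analyse it in the same way.

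The cost is plan wording and, optionally, one survey item. The week-split form uses only half of each phase's CPD days as outcome, in an exploratory analysis; the day-level form avoids that loss. Adjustment for prior CPD deals with earlier smoking driving the mediator but not with other unmeasured common causes, so the results should still be reported as exploratory.

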### Power and Sample Size

Our power analyses were conducted using a sample size of n=140 total participants. However, we will recruit and randomize n=164 because we expect a 15% drop-out rate by Week 6, based on the attrition rate of our existing EC product switching protocol (2015-0638). To demonstrate that we have adequate statistical power to detect likely effect sizes with n=140, we conducted power analyses for Aim 1 (i.e., the main effect of SREC type) and Aim 2 (i.e., the interaction between gender and SREC type) on our primary outcome measure, CPD collected from TLFB. However, in our attempt to estimate likely CPD effect size differences by gender as a function of SREC exposure (Aim 2), we were limited because there were no published studies that reported gender differences in CC and EC product use among CC smokers who were switched to nicotine and/or placebo ECs. Instead, to estimate the effect size of switching from CCs to ECs on CPD, we used a study  that examined the impact of switching to 18 mg ECs over 2 weeks that found that participants reduced their CPD by 96.3% (16.2 to 0.6 CPD). This allowed us to estimate the impact of switching to an EC with nicotine amounts similar to that of the SREC. To estimate the impact of product nicotine dose and gender on CPD, we used a study  that examined the impact of switching CC smokers to either VLNC (0.05 to 0.09 mg nicotine yield) CCs alone or combined VLNC cigarettes and NRT (21 mg patch). While this study did not include ECs, it allowed for the examination of the impact of nicotine on CPD, by gender, and found that men in the nicotine group (VLNC+NRT) smoked less VLNC CCs at week 2 than women .

Because of the absence of reliable effect sizes of the interaction effect under study in the literature, we estimated power for a series of effect sizes for both the direct and indirect effect. To perform the power analysis we first generated the matrix for our crossover design using the "samplingDataCRT" R package to sample data that reflects our prospective analysis. After generating the sample data, we calculated power for both the main effect of SREC type on CPD (Aim 1) and the SREC type by gender interaction (Aim 2) using three steps: 1) generate new CPD values from the crossover model defined above, 2) refit the model to the simulated data, and 3) evaluate the true positive success rate using the "simr" package . We ran 1000 simulations for each estimation for a series of effect sizes and for both the main effects and interaction models. **Figure 2** presents the power curves of these analyses. For the gender by SREC type interaction (Aim 2), **Figure 2** indicates that we have 80% power to detect a difference of 3.5 CPD or larger between the genders during SREC-NIC. For the SREC type main effect (Aim 1), **Figure 2** (inset) indicates that we have 80% power to detect a difference of 1.75 CPD or larger between SREC-NIC and SREC-PLA. The minimal detectable effect size is larger for the interaction effect compared to the main effect due to the increased power required to detect subgroup effects in randomized trials . Since the main modeling framework is linear, the interaction effect under study has an additive interpretation, such that the combined effects of SREC-NIC and being male contributes more to CPD reduction than the individual effects of the two factors. Additive interaction effects are more relevant for public health decision making and require a lower sample size than multiplicative interaction effects . In conclusion, our proposed sample size of 140 provide enough power to detect a CPD change of 1.75 for the main effect of SREC type and a CPD reduction of 3.5 for the proposed interaction effect, which we believe will be adequate to detect the likely differences we would observe.

## Potential Problems & Alternative Strategies

[figure not shown]
It is possible that the NIDA SREC use rates and product acceptability may be low in this study. Potential reasons for this have been described above, including (1) a lack of SREC flavors other than nicotine despite evidence that most EC users prefer flavors other than tobacco, (2) a lack of menthol SREC flavoring despite the ubiquity of menthol CC use among ethnically diverse populations, and (3) a level of nicotine in the SREC-NIC that, while comparable to other commercial ECs, may produce nicotine pharmacokinetics that are less reinforcing for DCS than those of CCs. One way to increase higher NIDA SREC use rates would be to incentivize their use, such as by paying participants a bonus if specific biomarkers indicated no CC product use (e.g., using anabasine, which is derived from tobacco and is not affected by EC use). However, we elected to evaluate NIDA SREC use without incentivizing it because we are seeking to provide NIDA with "naturalistic" information about SREC use and acceptability, as dependent variables, among a diverse sample of male and female adult CC smokers. We believe that even if SREC use and acceptability are low, this information would be of importance to NIDA.

The lengths of the SREC dose phases (2 weeks each) could be insufficient to determine stable responding. However, one study that switched CC users to ECs, using a within-subjects design, found that 2 weeks product exposure resulted in significant associations between EC nicotine dose and CPD, EC product use, and craving. Additionally, in our prior TCORS study we observed that most changes occurred within the initial 2 weeks of product use among CC smokers who were administered experimental CCs, including VLNC cigarettes. These findings suggest that 2 weeks of SREC exposure should be adequate to capture changes in response to switching to these novel nicotine products.

Despite the lack of a menthol-flavored SREC, we decided to include menthol smokers in this study. A significant number of minority CC smokers prefer menthol, and preliminary evidence suggests that adult menthol CC smokers prefer menthol over tobacco-flavored ECs. Additionally, menthol smokers typically represent ~55% of the community participants recruited for our non-treatment-seeking nicotine studies. Thus, to exclude menthol smokers would reduce the generalizability of the SREC findings in terms of use and acceptability.

This proposal will not include biochemical confirmation of menstrual phase or hormonal contraception use, and instead will rely upon self-report (e.g., menstrual phase estimated from start of last menstrual period), unlike other similar studies. In studies that use biochemical verification, most use serum measures of progesterone and estradiol levels to more precisely differentiate the luteal from the follicular phase. We also will not exclude women using

**Figure 2.** Power Curves (and 95% confidence intervals) for the Gender by SREC type Interaction Effect (Aim 2; main plot) and for the main effect of SREC type (Aim 1; inset plot).

hormonal contraception, despite the impact of such contraception on the menstrual cycle. We elected not to collect serum hormone levels at each phase because we do not want to burden or expose participants to the risks associated with 4 blood draws for what we consider to be exploratory factors in this project. Similar reasoning led us to not exclude women taking

**Table 3.** Study Timeline.

Study Milestone	Completion Month
IRB Approval of Protocol, Database Construction	3 Months
Finalize SOPs, Source Documents, and Staff Training	6 Months
First Participant Enrollment	6 Months
Final Participant Enrollment	20 Months
Complete Final Participant Follow-up	22 Months
Data Analysis & Manuscript Drafting	24 Months

that use of a closed-tank ECIG device among adult smokers results in relatively few adverse events. In this protocol (2015-0638; R01DA042526), which is ongoing, we are testing the strategy of simultaneously providing a smoker uninterested in quitting with both VLNCs as well as an ENDS product to determine if they will compensate for the reduction in nicotine from the VLNC's with the ENDS product. This is critical to the regulatory strategy aimed at determining nicotine levels in future ENDS product, because we may wish to maximize compensation in order to move people away from combustibles and increase the likelihood of cessation. Thus far, we have exposed 176 adult smokers to NIDA's VLNC combustible cigarette for up to 9 weeks and to commercially available closed-tank electronic cigarettes for up to 6 weeks (the same product being used in many other studies across the country). In terms of adverse events, similar proportions of participants have reported adverse events during the exclusive cigarette phases (18.0%) than during the phase where they are encouraged to use electronic cigarettes instead of smoking (15.3%). The most frequently reported adverse events during the electronic cigarette phases included depressive symptoms (n=4), sore throat (n=3), diarrhea (n=2), toothache (n=2), and vomiting (n=2). For the exclusive cigarettes phases, the most common adverse events included cough (n=6), irritability (n=5), headache (n=4), back pain (n=2), diarrhea (n=2), limb edema (n=2), insect bite (n=2), nausea (n=2), panic attack (n=2), and urinary tract infection (n=2). No severe adverse event was reported during the electronic cigarette phases, but one was reported during the exclusive cigarette phases, brachycardia (n=1). None of these were determined to be of probable or definitive relation to the study product. No serious respiratory symptoms have been reported. Our retention rate through the end of study has been 77%. The preliminary findings suggest that closed-tank electronic cigarettes are not associated with more adverse events than smoking combustible cigarettes.

**Consideration of Relevant Biological Variables.** We will recruit an equal number of male and female adult daily smokers for this study because gender differences form the main focus of this proposal. While biological sex is the primary independent variable, we will also account for other relevant biological variables, such as age, by including them as covariates of interest in our statistical models. We are using multilevel models to partially pool the estimate from each covariate toward the overall mean of all estimates. This is a natural away to account for multiple comparisons without sacrificing power (which we do in the case of Bonferroni correction). Each effect is shrunk toward the overall estimate. The higher the uncertainty of a specific effect the more it shrinks toward the overall estimate.

**Timetable.** After a 3-month study setup, we expect to enroll between months 6 and 20, at a rate of 10 subjects per month (see **Table 3**). The final participant session will be during month 22, and data analysis and initial manuscript drafting will occur by month 24.

**Future directions.** At the project's conclusion, we will be able to provide scientific information on gender differences in terms of the extent to which the NIDA SREC is used and accepted by adult CC smokers, which would indicate whether it could serve as a good model of future EC research. We will also identify factors that moderate or mediate the effects of switching to nicotine and placebo SRECs from CCs. Our next steps will be to submit proposals

hormonal contraception. However, we will capture self-report of both factors and use them as moderators (hormonal contraceptive use) and mediators (menstrual phase) as part of the exploratory aim.

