## Participants

We will recruit up to 196 participants (98 male and 98 female adult CC smokers) from the state of Texas and/or Houston metropolitan areas. Inclusion/exclusion criteria are described in **Table 1**. Note: For the purpose of eligibility requirements and ongoing smoking status, "cigarettes" will also include the tobacco product that is commonly known as "little cigars". Little cigars are machine-manufactured and sold in packs similar to cigarettes. They are often smoked by individuals of limited means because they are cheaper than conventional cigarettes.

COVID-19 adaptation: While this study is being conducted virtually, we will expand participant recruitment to the state of Texas.

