### Statistical Approach & Expected Outcomes

**General Data Analytic Strategy.** To analyze our aims, we will use a crossover design model with  $n = 140$  subjects (assuming 15% attrition of  $n=164$ ) and  $k = 3$  periods. In this design,  $t_0$  and  $t_1$  will be the two SREC types, with  $t_0$  for SREC-PLA and  $t_1$  for SREC-NIC. We will use the following model for  $y$  (e.g., CPD):  $y_{ij} = b_1 + b_{2t(i,j),t(l,j-1)} + e_{ij}$ , where  $b_1$  is the effect of subject  $i$ , and  $b_2$  is the effect of treatment  $t_{10}$  when preceded by treatment  $t_{10}$ .  $T(i,j)$  is the treatment assigned to subject  $i$  in period  $j$ , for  $1 \leq i \leq n$  and  $1 \leq j \leq k$ . The residual errors  $e_{ij}$  are assumed to be independent and identically distributed with expectation 0 and variance  $\sigma^2$ . In this design, each subject will act as its own control reducing the influence of confounding, reducing variance and improving accuracy and sensitivity for the estimated effect of interest. In the interaction models (Aim 2), gender will be entered in the equation and interacted with  $b_{2t(i,j),t(l,j-1)}$  to estimate gender by treatment interaction effects on all outcomes. Period and carryover effects will be evaluated by testing equivalence of effects across time (e.g., CPD collected using TLFB). We will utilize a mixed model approach for estimation using the "glmer" function of the "lme4" R package. Missingness will be treated as missing-at-random within maximum likelihood estimation and we will utilize not-missing-at-random approaches (e.g., pattern mixture model) if non-ignorable missingness is suspected. Given the large number of outcomes, the analyses will address issues of multiplicity by applying the False Discovery Rate.

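### The enrolment timetable (10 per month, months 6 to 20) yields about 140 to 150 people, short of the 164 the sample size section says will be randomised

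*Combined protocol and SAP*

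**What the plan says.** All places are in the combined protocol and SAP, section D.

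- **Timetable paragraph** (under Potential Problems & Alternative Strategies): "we expect to enroll between months 6 and 20, at a rate of 10 subjects per month". It puts the final participant session in month 22, and data analysis and first drafting of manuscripts by month 24.
- **Table 3**: the milestone "Final Participant Enrollment" is set at month 20, the end of follow-up at month 22 and analysis at month 24.
- **Power and Sample Size**: "Our power analyses were conducted using a sample size of n=140 total participants", and then "we will recruit and randomize n=164 because we expect a 15% drop-out rate by Week 6". The section states 80% power for 1.75 CPD (Aim 1) and 3.5 CPD (Aim 2).
- **General Data Analytic Strategy**: repeats 140 analysed out of 164, and specifies a mixed model fitted by maximum likelihood under missing-at-random.
- **Participants**: "We will recruit up to 196 participants".
- **Phases 2 & 3 paragraph** (under Procedures): equates half of those randomised with 70 subjects, which implies 140 randomised.

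**The concern.** The sample size section allows for drop-out by randomising 164 to keep 140. The timetable makes no such allowance: over 14 months it yields 140 people before anyone has left. The schedule and the sample size cannot both be met as written.

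What is at stake is mainly practical. A team that tracks accrual against 10 per month will look on target up to month 20 and then find itself short. It would have to extend enrolment past the milestones that follow, or stop with fewer people than the design calls for. The protocol describes the funding call as a two-year one, and its own plan ends at month 24, so the schedule has little room for an extension.

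**Working it through.** **Inputs from the documents:** 10 per month; months 6 to 20; 164 randomised; 15% drop-out by week 6; 140 analysed; 80% power at 1.75 and 3.5 CPD; last session in month 22. The 15% is taken as given.

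**1. The plan's own sample size.** 164 x 0.85 = 139.4, about 140. In reverse, 140 / 0.85 = 164.7. The 164 is reproduced within rounding.

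**2. What the timetable yields.**
- 14 months elapsed: 10 x 14 = 140, which is 164 - 140 = 24 short.
- 15 months, with months 6 and 20 both counted in full: 10 x 15 = 150, which is 164 - 150 = 14 short.

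**3. What 164 would need.**
- Rate by month 20: 164 / 14 = 11.7 per month, or 164 / 15 = 10.9.
- Time at 10 per month: 164 / 10 = 16.4 months. Counting from month 6, enrolment ends at 6 + 16.4 = 22.4. On the inclusive count it starts one month earlier and ends at 5 + 16.4 = 21.4.
- Last week-6 visit: six weeks is about 1.4 months, so 21.4 + 1.4 = 22.8 to 22.4 + 1.4 = 23.8. Both are later than month 22.

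**4. Power if enrolment did stop at month 20.** The 80% cannot be recomputed from the text, which gives no alpha, standard deviation or within-person correlation. It is used here as an anchor, with two-sided alpha 0.05 as an assumption:

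Power(n) = Phi[(1.960 + 0.842) x sqrt(n/140) - 1.960]

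The same scaling serves both aims. The Aim 1 figure implies a standard deviation of the within-person difference of 1.75 x sqrt(140) / 2.802 = 7.39, and with 70 per gender that value returns 80% at 3.5 CPD. The detectable difference scales with sqrt(140/n).

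| Enrolled | Completers (x 0.85) | Power | Detectable at 80%, Aim 1 / Aim 2 |
|---|---|---|---|
| 140 | 119 | Phi(2.583 - 1.960) = 73% | 1.90 / 3.80 CPD |
| 150 | 127.5 | Phi(2.674 - 1.960) = 76% | 1.83 / 3.67 CPD |

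**5. Allowing for partial data.** The table gives drop-outs no weight. The most favourable case for the plan is that every drop-out leaves after Phase 2 and contributes baseline and Phase 2 data. For Aim 1, the variance of the treatment contrast was computed under a random-subject model with period and treatment effects, for within-person correlations of 0.3 to 0.9. Power is then Phi[2.802 x sqrt(V0/V) - 1.960], where V0 is the variance with 140 complete and V the variance with the drop-outs partly observed. This gives about 75% to 76% for 140 enrolled (119 complete, 21 partial) and 78% to 79% for 150 enrolled (127.5 complete, 22.5 partial).

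**The case against.** The best defence is that the timetable is an expectation and Table 3 a list of milestones. Nothing in the documents closes enrolment at month 20 whatever the count, whereas the sample size section does commit to 164. On that reading the trial runs 1.4 to 2.4 months longer and loses no power. This stands as far as power goes. It does not remove the inconsistency, because step 3 shows that the extension breaks the month-22 milestone and needs a revised schedule.

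Three stronger readings are tempting, and the documents do not support them.

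- **That 140 enrolled instead of 164 shows the 80% power to be wrong.** The 80% is calculated at exactly 140 analysed. Power falls only if a further 15% is lost from the 140 and enrolment does stop. The figure near 73% also rests on an assumed alpha and on drop-outs contributing nothing, although the planned model uses their data.
- **That the schedule also fails a target of 196.** The number is given as an upper limit, so falling short of it breaches nothing and has no bearing on power.
- **That 196 is a consent figure from which 164 are randomised, making the shortfall worse.** No section says so or gives a loss between consent and randomisation. If enrolment here does count people before randomisation, the shortfall would be larger, but the documents do not allow it to be sized.

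**Conclusion.** The point holds as a mismatch between the schedule and the sample size. The timetable delivers 140 to 150 people against 164 to be randomised, and at the stated rate 164 is not reached until about month 21.4 to 22.4, too late for the last week-6 visit to fall by month 22. This part needs only the documents' own figures and a choice of how to count months.

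The power loss is conditional and moderate. It arises only if enrolment ends at month 20 at 10 per month. Power is then about 73% to 76% counting completers alone, and up to about 75% to 79% with partial data, on an assumed two-sided alpha of 0.05. The 80% at 140 analysed stands as a conditional statement.

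**What to change.** In the Timetable paragraph and Table 3, do one of the following:

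- state the rate needed to randomise 164 by month 20, about 11 to 12 per month; or
- keep 10 per month and move the milestones. Shifting all of them by the same 1.4 to 2.4 months puts the end of enrolment at about month 21.4 to 22.4, the end of follow-up at 23.4 to 24.4 and analysis at 25.4 to 26.4.

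Only if enrolment will in fact stop at month 20 at 10 per month, add to Power and Sample Size that about 119 to 127 completers are expected. Give the resulting power (about 73% to 76%) and detectable differences (about 1.8 to 1.9 and 3.7 to 3.8 CPD), and state the alpha used. The existing statement for 140 analysed need not change.

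In the same edit, reconcile 140, 164 and 196 across Participants, the Phases 2 & 3 paragraph, General Data Analytic Strategy, Power and Sample Size, and Timetable. Say whether enrolled means consented or randomised, and what the ceiling of 196 is for.

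The document change is a text correction. The design and analysis stay as they are. The real cost is either somewhat faster recruitment or a schedule that runs past month 24.
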